12.6.4 Efficacy

The primary efficacy hypothesis for this study is that there are no clinically meaningful differences between ABP 798 and rituximab in ORR by week 28. Clinical equivalence will be demonstrated by first comparing the 1-sided 95% lower confidence interval (CI) limit of the RD of ORR by week 28 between ABP 798 and rituximab with a noninferiority margin of -15%. If this is successful, the 1-sided 95% upper CI limit of the RD of ORR by week 28 between ABP 798 and rituximab will be compared with a nonsuperiority margin of +35.5%. In addition, a 2-sided 95% CI will be calculated and evaluated against a symmetrical margin of 15% for noninferiority and nonsuperiority. The CIs for RD will be estimated using a generalized linear model adjusted for the stratification factors.

The primary analyses of ORR will be conducted based on central, independent, blinded radiologists' assessments on the FAS according to randomized treatment. The sensitivity analysis will be conducted based on central, independent, blinded radiologists' assessments on the per-protocol analysis set according to actual treatment received and based on the Investigator's assessment of disease on the FAS according to randomized treatment.

Determination of response is outlined in [Section 17.2](#).

Inferential analyses will only be performed for the primary endpoint. The secondary endpoints RD of ORR at week 12 will be summarized descriptively.

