- Percentage of subjects with complete depletion of CD19+ cell count from baseline to study day 8 and total IgG and IgM antibody levels
- Serum concentrations at predose and immediately after the end of infusion at week 12

Safety Criteria:

- Treatment-emergent adverse events (AEs) and serious AEs (SAEs)
- Clinically significant changes in laboratory values and vital signs
- Incidence of antidrug antibodies
- On study progression-free survival (PFS)
- On study overall survival (OS)

STATISTICAL METHODS:

Clinical equivalence of the primary endpoint will be demonstrated by first assessing non-inferiority by comparing the 1-sided 95% lower confidence interval (CI) limit of the RD of ORR by week 28 between ABP 798 and rituximab with a -15% margin. If the test of non-inferiority is successful, then the study will sequentially assess non-superiority by comparing the 1-sided 95% upper CI limit of the RD of ORR by week 28 with a 35.5% margin. Additionally, a 2-sided 95% CI will be calculated and evaluated against a symmetrical margin of 15% for noninferiority and nonsuperiority. The CIs for RD will be estimated using a generalized linear model adjusted for stratification factors. Analyses of efficacy endpoints will be conducted on the full analysis set (consisting of all randomized subjects) according to randomized treatment.

In addition, categorical variables will be summarized using the number and percentage of subjects falling into each category. Continuous variables will be summarized using mean, standard error or standard deviation, median, minimum, maximum, and number of subjects with observations.

Pharmacokinetics endpoints will be summarized as point estimates of the geometric mean ratio and 90% CIs of test (ABP 798)-to-reference (rituximab). The pharmacodynamic endpoint of percentage of subjects with complete depletion of CD19+ cell count from baseline to study day 8 will be summarized descriptively. Pharmacokinetics and pharmacodynamic endpoints will be conducted on safety analysis set (consisting of subjects receiving at least 1 dose of IP) according to actual treatment received.

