6.4 Study Rationale

Similarity of ABP 798 to rituximab has been shown using bioanalytical methods and pre-clinical studies (refer to the Investigator's Brochure for additional information). As outlined in the guideline on similar biological medicinal products containing monoclonal

antibodies ([EMA/CHMP/BMWP/403543/2010](#)), applicants are expected to provide data on similarity of pharmacokinetics (PK)/pharmacodynamics, safety, and efficacy.

In the US, EU, and much of the world, laws, regulations, and guidances have been or are being put in place to increase availability of biological treatments by developing and licensing biosimilar products ([CHMP/437/04 Rev 1](#); [EMA/CHMP/BWP/247713/2012](#); [EMA/CHMP/BMWP/42832/2005 Rev 1](#); [US FDA 2012a](#); [US FDA 2012b](#)).

A biosimilar product, generally, is one that is highly similar to a licensed biologic reference product, and there are no clinically meaningful differences between the biosimilar and reference product in terms of safety, purity, and potency. Biosimilarity is demonstrated by the totality of the evidence, including quality, nonclinical, and clinical evidence. The quality and nonclinical data for ABP 798 and rituximab are summarized in the Investigator's Brochure. The current study is designed to evaluate efficacy, PK, and safety, specifically, to demonstrate that there is no clinically meaningful difference between ABP 798 and rituximab in terms of overall response rate (ORR), peak and trough drug concentration, complete depletion of CD19+ cell count, safety, and immunogenicity.

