8.1 Overall Study Design and Plan

This is a randomized, double-blind study in adult subjects with Grade 1, 2 or 3a follicular B-cell NHL and low tumor burden. Approximately 250 subjects (125 per treatment group) will be randomized (1:1) to receive investigational product (IP) (ABP 798 or rituximab) at a dose of 375 mg/m² administered as an intravenous (IV) infusion once weekly for 4 weeks followed by dosing at weeks 12 and 20. Tumor assessment will be performed at baseline and weeks 12 and 28. Subjects will be stratified by geographic area and age (> 60 vs ≤ 60 years).

A subject will remain in the treatment phase until week 28. Subjects who discontinue IP before week 20 will be followed for 8 weeks after the last dose of IP and then complete the end-of-study (EOS) visit.

An independent data monitoring committee (DMC) will evaluate the safety data throughout the study, including an initial safety review after the first 12 subjects have received at least 2 doses of IP.

Figure 1. Study Diagram

* Response assessments at study weeks 12 and 28
Wk = week

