1. INTRODUCTION

This statistical analysis plan (SAP) describes the statistical methods to be used during the reporting and analyses of data collected under Amgen Inc. Protocol 20130109, titled “A Randomized, Double-Blind Study Evaluating the Efficacy, Safety, and Immunogenicity of ABP 798 Compared with Rituximab in Subjects with CD20 Positive B-cell Non-Hodgkin Lymphoma (NHL).”

This SAP should be read in conjunction with the study protocol and electronic Case Report Forms (eCRFs). This version of the plan has been developed using the protocol dated 07 January 2016 version 3.0 and eCRFs dated 17 SEP 2014. Any further changes to the protocol or eCRFs may necessitate updates to the SAP.

The SAP is to be developed in two stages. The purpose is to “finalize” a SAP so that programming can start earlier in the process. Versions of the SAP up to initial sponsor approval will be known as SAP1. SAP1.1 is issued to reflect protocol version 3.0. Changes following approval of SAP1.1 will be tracked in the SAP Change Log and a final version of the SAP, known as SAP2, will be issued for Amgen’s approval prior to database lock.

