9.5 EFFICACY ANALYSES

9.5.1 Primary Variable

9.5.1.1 PRIMARY ANALYSIS

The primary analysis of ORR by week 28 will be based on the FAS according to randomized treatment, using data from the central, independent, blinded radiologists' and oncologist's assessments.

Clinical equivalence of the primary endpoint will first be demonstrated by comparing the 1-sided 95% lower confidence limit of the RD of ORR by week 28 between ABP 798 and rituximab with a noninferiority margin of -15%. If this is successful, the 1-sided upper 95% confidence limit of the RD of ORR by week 28 will be compared with a nonsuperiority margin of +35.5%.

To estimate the 1-sided 95% confidence limits of the RD of ORR by week 28, the generalized linear model adjusted for the stratification factors (geographic region and age group) will be fitted using the SAS[®] procedure "GENMOD". A sample SAS code fragment is provided below for reference:

```
proc genmod data=<data> descending;  
  class trt <categorical_var>;  
  model <binary var> = trt <categorical_var> stratification factors
```

```
<categorical_var>/ dist=binomial link=identity;  
estimate 'label of the estimate' trt -1 1 / alpha=0.1 ;  
run;
```

In addition, a 2-sided 95% confidence interval (CI) will be calculated and evaluated against a symmetrical margin of 15% for noninferiority and nonsuperiority.

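### Does the +35.5% nonsuperiority margin leave clinical equivalence without a working upper bound?

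*Protocol*

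**What the plan says.** The hypothesis in Protocol 12.6.4 is two-sided: "there are no clinically meaningful differences between ABP 798 and rituximab in ORR by week 28". Protocol 6.4 states the aim in the same terms.

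The deciding rule is sequential and asymmetric. The 1-sided 95% lower limit of the RD is compared with -15%. If that succeeds, Protocol 12.6.4 turns to the 1-sided 95% upper limit, which "between ABP 798 and rituximab will be compared with a nonsuperiority margin of +35.5" percent. SAP 9.5.1.1 agrees: "the 1-sided upper 95% confidence limit of the RD of ORR by week 28 will be compared with a nonsuperiority margin of +35.5" percent; the Protocol Synopsis has the same step. The limits come from a binomial identity-link model adjusted for region and age, fitted to all randomized subjects.

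Protocol 12.6.4 then adds: "In addition, a 2-sided 95% CI will be calculated and evaluated against a symmetrical margin of 15% for noninferiority and nonsuperiority". SAP 9.5.1.1 repeats this. Neither section says what follows if that check is met or missed. SAP 9.9 does use the interval: for Japan, equivalence of efficacy is judged on a 2-sided 95% CI for the RD, with no margin restated there.

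The sample size is about 250, 125 per arm (Protocol 8.1). The text behind it in Protocol 12.2 is redacted, so the expected ORR and any rationale for +35.5% cannot be seen.

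**The concern.** An RD cannot exceed 100% minus the rituximab ORR. If the true rituximab ORR is above 64.5%, a true RD of +35.5% is impossible, so the second step tests a null hypothesis that cannot hold. In observed data the step becomes automatic at a somewhat higher rate. A conclusion worded as equivalence would then be a noninferiority conclusion, although the hypothesis is two-sided and the plan itself treats a higher response as something to rule out.

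The two criteria can also conflict. With 89/125 responders on rituximab and 120/125 on ABP 798, both steps pass while the 95% CI lies entirely above +15%. The main decision rule would call this equivalence and attach no consequence to the failed ±15% check.

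**Working it through.** **Inputs.** n = 125 per arm (Protocol 8.1); margins -15%, +35.5% and ±15% (Protocol 12.6.4); limits at 1.645 SE for the 1-sided 95% level and 1.96 SE for the 2-sided 95% level. Assumption: unadjusted Wald limits, SE = √[pR(1-pR)/125 + pT(1-pT)/125]. The expected ORR is redacted, so a range is shown.

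**The plan's own figure.** N = 250 cannot be reproduced without the expected ORR and power. For noninferiority alone, n = 2p(1-p)(1.645 + zβ)²/0.15² gives 126 per arm at p = 0.65 with 80% power (zβ = 0.842), and 122 at p = 0.80 with 90% power (zβ = 1.282). So 125 per arm is compatible with several expected rates.

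**Where the second step stops being able to fail.** The largest upper limit occurs at 125/125 on ABP 798.
- Rituximab 88/125: 0.296 + 1.645 × 0.0408 = 0.3632, above 0.355. ABP 798 counts of 124 and 125 fail.
- Rituximab 89/125: 0.288 + 1.645 × 0.0405 = 0.3546, below 0.355. No count fails.

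Clearance at 89 is only 0.04 points. Newcombe and Miettinen-Nurminen limits move the threshold to 90/125 (72.0%), and arm sizes of 115 to 135 put it between 71.1% and 72.2%. In a few simulated tables, the adjusted model moved the upper limit by 1 to 2 points, and by about 4 in one. The threshold is therefore about 71-72%, not an exact count.

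**The ±15% check has the same property.** Its largest upper limit on the 2-sided 95% CI is 15.75% at 112/125 and 14.76% at 113/125. From about 90% ORR its upper side cannot fail either.

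**Operating characteristics at RD 0**, enumerating all 126 × 126 outcomes:

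| True ORR | Step 1 met | Steps 1 and 2 met | ±15% met (95% CI) | P(rituximab ≥ 89/125) |
|---|---|---|---|---|
| 50% | 0.7567 | 0.7567 | 0.3419 | 0.0000 |
| 60% | 0.7823 | 0.7823 | 0.3528 | 0.0061 |
| 70% | 0.8271 | 0.8271 | 0.4760 | 0.4276 |
| 80% | 0.9066 | 0.9066 | 0.6911 | 0.9932 |
| 90% | 0.9885 | 0.9885 | 0.9494 | 1.0000 |

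The second and third columns agree to four decimals throughout, including at 50%, where the second step can still fail. Step 2 overturns a step 1 success with probability of at most 0.003% at RD 0. At RD +10 the figure is 0.7% (ORR 50%), 0.1% (70%) and 0.004% (80%); at RD +20 it is 17%, 6.6% and 0.7%. The step guards against large superiority at moderate response rates and little else. That comes from a wide margin, not from a defect that begins at 71%.

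**The conflicting example.** For 120/125 against 89/125, RD = 0.248 and SE = √(0.712 × 0.288/125 + 0.96 × 0.04/125) = 0.0441. The 90% CI is 17.5% to 32.1% and the 95% CI is 16.2% to 33.4%. The probability that both steps are met with the 95% CI wholly above +15%, at its largest over ORR 50% to 95%, is 0.0001% at RD 0, 0.005% at RD +5 and 0.14% at RD +10.

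**The case for a change.** The strongest case for a change looks at a true RD of +15, the edge of the plan's own symmetrical margin. There the deciding rule concludes equivalence with probability 97% (ORR 60%), 99% (70%) and 99.9% (80%), against 2% to 5% for the ±15% check. The criteria also part company when the products are truly equal: both steps are met but ±15% is not in 43% of trials at ORR 60%, 35% at 70% and 22% at 80%. Every outcome that meets ±15% also meets both steps, so ±15% could become a third step in the sequence without spending alpha, and SAP 1 says "a final version of the SAP, known as SAP2, will be issued" before database lock.

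The arithmetic stands, and so does the observation that the main rule attaches no consequence to the ±15% check. The inference to a needed change does not.
- Because ±15% is nested, making it the third step would make it the sole decider of equivalence; +35.5% would no longer matter to that conclusion.
- On the 95% CI it would also tighten the lower side from 1-sided 5% to 2.5%, which has nothing to do with the upper bound.
- The splits under equality are mostly failures of the interval to exclude 15 points in one direction. They are not evidence of a difference.
- Whether +35.5% is too wide cannot be judged while the text that may support it is redacted.

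A milder request, a sentence saying that at high response rates the conclusion rests on the lower limit, would disclose arithmetic that any reader can do and would alter no result.

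**Conclusion.** The observation is right, but the plan need not change. With about 125 per arm and unadjusted limits, the +35.5% step cannot fail from an observed rituximab ORR of about 71-72%, and under equality it has almost no effect at any ORR from 50% up. Whether the trial falls in that range depends on the redacted expected ORR.

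The margin is stated openly, the sequence is prespecified, and the stricter ±15% evaluation is planned alongside it, so a reader of the results will have both. The lower side, which guards against a less effective product, is unaffected: at a true RD of -15 the rule succeeds 5% to 6% of the time. The troubling outcome, equivalence declared with a 95% CI wholly above +15%, needs a true advantage well beyond 10 points to be more than a rarity, and Protocol 6.3 describes a product with the same amino acid sequence as its reference.

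The alternative has a real price. At RD 0, success falls from 83% to 65% (90% CI) or 48% (95% CI) at ORR 70%, and from 91% to 81% or 69% at ORR 80%. A sponsor may reasonably decline that trade. The margin left unstated in SAP 9.9 is a small gap that analysts will fill sensibly, since ±15% is the only margin the plan pairs with a 2-sided 95% CI.

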12.6.5 Pharmacokinetics

The 90% CI for the geometric mean ratio (GMR) of test (ABP 798)-to-reference (rituximab) for serum concentrations at predose (trough) and immediately after the end of infusion at week 12 will be calculated. Point estimates and CIs for the GMR will be estimated from an analysis of covariance model. The analysis will be conducted on the safety analysis set according to actual treatment received. Additional details on the PK analysis will be provided in the SAP.

12.6.6 Pharmacodynamics

Pharmacodynamic endpoints (complete depletion of CD19+ cell count from baseline to week 2 (day 8), total IgG and IgM antibody levels) will be summarized descriptively for the safety analysis set by actual treatment received.

12.6.7 Safety

Safety will be assessed in the safety analysis set with treatment assignment based on actual treatment received. Independent safety reviews will be performed by the DMC periodically throughout the study, including an initial safety review after the first 12 subjects have received at least 2 doses of IP. Blinded study data will also be monitored on an ongoing basis by the blinded clinical study team to ensure subjects' safety. Safety analysis will include analyses of drug exposure, AEs, PFS and OS, clinical laboratory tests, vital signs, ECGs, and antidrug antibodies.

12.6.7.1 Investigational Product Administration

For the IP (ABP 798 or rituximab), summary statistics will be provided for the total number of doses and total duration of IP exposure throughout the study.

12.6.7.2 Adverse Events

All verbatim terms for any reported AEs will be coded to the appropriate system organ class and preferred term according to the current version of the MedDRA dictionary, and graded by the Investigator for severity as per CTCAE version 4.03. The number and percentage of subjects reporting AEs (all, serious, treatment related, and deaths) will be reported.

Only treatment-emergent AEs will be summarized. Treatment-emergent events are those that begin or increase in severity or frequency at or after the time of first treatment up to the EOS visit. All treatment-emergent AEs will be summarized by treatment arm and according to the MedDRA system organ class (SOC) and preferred term.

Summaries will be provided for the incidence of all treatment-emergent AEs by severity. Additional summaries will be presented for SAEs. All AE data will be listed by subject, and a separate listing will include all SAEs, including any deaths on study.

Adverse events of interest ([Section 11.3](#)) will be summarized by treatment arm and preferred term.

12.6.7.3 Immunogenicity

The number and percentage of subjects developing antidrug antibodies and those developing neutralizing antibodies will be tabulated for each treatment.

12.6.7.4 Progression-free Survival and Overall Survival

Progression-free survival is defined as the time from randomization until the first occurrence of disease progression or death from any cause according to the standard criteria in [Cheson et al, 1999](#). For subjects alive and progression-free at the week 28/EOS visit, PFS will be censored at the date of the last tumor evaluation demonstrating lack of progression.

Overall survival is defined as the time from randomization to death from any cause. Subjects who have not died before the week 28/EOS visit will be censored for OS at the last known date alive on or prior to EOS.

For these time-to-event outcomes, the hazard ratio and 1-sided 95% and 97.5% CIs for ABP 798 relative to rituximab will be estimated from a Cox model stratified by stratification factors. In addition, Kaplan-Meier curves and median survival time will be provided descriptively.

12.6.7.5 Concomitant Medications and Therapies

Concomitant medications will be coded by WHO Drug Dictionary and will be summarized by treatment group with number and percentage of subjects receiving each category of medication.

12.6.7.6 Clinical Laboratory Test

Clinical laboratory test results and change from baseline will be summarized by time point. In addition, shift tables, from baseline to the worst on-study laboratory toxicity based on CTCAE v4.03 grading, will be presented.

12.6.7.7 Vital Signs and Physical Examinations

Vital sign data (observed and change from baseline) will be summarized using descriptive statistics by time point and treatment. Abnormal findings from physical examinations will be listed by subject and assessed for clinical significance and included in the AE listings and summaries.

12.6.7.8 Electrocardiograms

Electrocardiogram results will be summarized using descriptive statistics.

12.6.8 Interim Analysis

A safety analysis will be performed by a DMC ([Section 12.6.9](#)) after the first 12 subjects have received at least 2 doses of IP.

No interim analyses of efficacy or pharmacodynamics are planned.

12.6.9 Data Monitoring Committee

A DMC external to Amgen and PRA will be formed with members consisting of individuals chosen for their expertise in follicular NHL. Members of the DMC will include, at a minimum, physicians external to Amgen and PRA, and appropriate statistical representation external to Amgen and PRA. The primary role of this independent DMC will be to monitor safety data.

The DMC will review unblinded safety data at regular intervals, as outlined in the DMC charter (approximately twice yearly; the first assessment will be when 12 subjects have received at least 2 doses of IP).

The DMC will communicate major safety concerns and recommendations regarding study modification or termination to Amgen management at any time during the conduct of the study.

Records of all meetings will be archived. Selected Amgen, or its designee, staff may serve as liaisons to the external DMC, but will not be voting members and will not be unblinded to the results. Details regarding the DMC will be provided in the DMC charter.

13 MONITORING PROCEDURES (QUALITY ASSURANCE)

Amgen has ethical, legal, and scientific obligations to conduct this study in accordance with established research principles and ICH GCP guidelines. As such, in order to fulfill these obligations and to maintain current of study progress, Amgen monitors, or Amgen's designees, will visit the investigative sites during study conduct, in addition to maintaining telephone and written communication. On-site visits, telephone calls, and regular inspection of the eCRFs will be conducted in order to assess subject enrollment, compliance with protocol procedures, completeness and accuracy of data entered on the eCRFs, verification of eCRF data against original source documents, and occurrence of AEs. The Investigator must provide the monitor with full access to all source and study documents.

13.1 Routine Monitoring

Amgen, or its designee, assigned monitors will conduct regular site visits to the investigational facilities for the purpose of monitoring various aspects of the study. The Investigator must agree to Amgen, or its designee, authorized personnel having direct access to the clinical (or associated) files and clinical study supplies (dispensing and storage areas) for all study subjects considered for study entry for the purpose of verifying entries made in the eCRF, and must assist with their activities, if requested. Adequate time and space for monitoring visits should be made available by the Investigator.

The site must complete the eCRFs in a timely manner and on an ongoing basis to allow regular review by the study monitor.

Whenever a subject name is revealed on a document that is to be collected for the Sponsor the name must be blacked out permanently by the site personnel, leaving the initials visible, and must be annotated with the subject number as identification.

